1.0 OBJECTIVES

1.1 Primary Objective(s)

To compare progression free survival (PFS) of patients with advanced melanoma refractory to an anti-PD-1 or anti-PD-L1 agent, treated with combination therapy ipilimumab plus nivolumab versus ipilimumab alone.

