7.5 Criteria for Removal from Protocol Treatment

- Progression of disease as defined in [Section 10.2d](#). However, the patient may continue to stay on protocol treatment as long as, in the opinion of the treating investigator, the patient is continuing to clinically benefit from treatment. This may occur if there are lesions that continue to respond to the therapy despite others progressing, or if there is symptomatic relief of symptoms on therapy.

- b. Completion of 4 cycles on Arm 1.
- c. Symptomatic deterioration (as defined in [Section 10.2e](#)).
- d. Unacceptable toxicity (see also [Section 8.0](#)).
- e. Treatment delay for any reason > 12 weeks.
- f. The patient may withdraw from the study at any time for any reason.

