8.2 General considerations

- a. No dose reductions are allowed.
- b. The maximum dose delay for any reason is 84 calendar days (12 weeks).
- c. Patients on IV steroids may be switched to an equivalent dose of oral corticosteroids (e.g., prednisone) at start of tapering or earlier, once sustained clinical improvement is observed. Lower bioavailability of oral corticosteroids should be taken into account when switching to the equivalent dose of oral corticosteroids.

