8.4 Dose Delay Criteria for Nivolumab in Combination with Ipilimumab (Arm 2)

Dose modifications for nivolumab in combination with ipilimumab by adverse event type are detailed in [Table 8.1](#). General considerations for dose modifications are as follows.

For the initial induction period, patients with Grade 2 or 3 events requiring discontinuation of treatment with the combination may consider continuing treatment with single agent nivolumab when the event resolves to baseline. However, patients with renal, CNS, or pulmonary toxicity must be removed from study.

- a. In addition to the AEs identified in the table below, ipilimumab and nivolumab dose should be delayed for any AE, laboratory abnormality or inter-current illness which, in the judgment of the treating investigator, warrants delaying the dose of study medication.
- b. Patients requiring a delay of > 6 weeks or who experience immune-related toxicity with inability to decrease prednisone ≤ 10 mg PO daily must go off protocol therapy entirely.
- c. Patients who received systemic corticosteroids for management of any drug-related immunologic toxicity must be off corticosteroids or have tapered down to an equivalent dose of prednisone 10 mg/day.
- d. Nivolumab monotherapy may be continued at treating investigator discretion if there is evidence of clinical benefit. In this event, patient will continue nivolumab until AE is resolved and ipilimumab may be re-started or if ipilimumab is permanently discontinued (in congruence with guidelines in table below), then patient will continue nivolumab alone until cycles are completed. At completion of 4 cycles, patient may continue on nivolumab alone, as per protocol. If ipilimumab is permanently discontinued prior to receipt of 4 doses, nivolumab dosing should remain at the Cycle 1-4 dosing (1 mg/kg every 2 weeks) until completion of Cycle 4 and should then switch to Cycle 5+ dosing (480 mg every 4 weeks).

Table 8.1 Dose Modification for Related Adverse Events

Treatment-related Adverse Event	Grade of Event	Nivolumab and/or Ipilimumab
Nausea	≤ Grade 1	No dose modification
	Grade 2	Hold until ≤ Grade 1 OR baseline (exceptions as noted below) ¹
	Grade 3	Off protocol therapy (exceptions as noted below) ¹
	Grade 4	Off protocol therapy
*Patients requiring a delay of >2 weeks must go off protocol therapy.		
Recommended management: antiemetics.		
Diarrhea (immune-related enterocolitis)	≤ Grade 1	No dose modification

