	Grade 2	Hold until ≤ Grade 1 OR baseline (exceptions as noted below) ¹
	Grade 3	Off protocol therapy (exceptions as noted below) ¹
	Grade 4	Off protocol therapy
*Patients requiring a delay of >2 weeks must go off protocol therapy		

Recommended management: Loperamide antidiarrheal therapy Dosage schedule: 4 mg at first onset, followed by 2 mg with each loose motion until diarrhea-free for 12 hours (maximum dosage: 16 mg/24 hours) Adjunct anti-diarrheal therapy is permitted and should be recorded when used. See GI AE Algorithm for management of symptomatic colitis. Patients with Grade 2 symptoms but normal colonoscopy and biopsies may be retreated after resolution. Patients who require steroids must be taken off study treatment. Please evaluate pituitary function prior to starting steroids if possible without compromising acute care. Evaluation for all patients for additional causes includes C. diff, acute and self-limited infectious and foodborne illness, ischemic bowel, diverticulitis, and IBD.
		
Vomiting	≤ Grade 1	No dose modification
	Grade 2	Hold until ≤ Grade 1 OR baseline (exceptions as noted below) ¹
	Grade 3	Off protocol therapy (exceptions as noted below) ¹
	Grade 4	Off protocol therapy
*Patients requiring a delay of >2 weeks must go off protocol therapy.		
Recommended management: antiemetics.		
Other GI	≤ Grade 1	No dose modification
	Grade 2	Hold until ≤ Grade 1 OR baseline (exceptions as noted below) ¹
	Grade 3	Off protocol therapy (exceptions as noted below) ¹
	Grade 4	Off protocol therapy
Patients with Grade 2 or 3 N-V should be evaluated for upper GI inflammation and other immune related events.		
Neurologic events (new,	≤ Grade 1	No dose modification
	Grade 2	Hold until ≤ Grade 1 OR baseline (exceptions as noted below) ¹

Treatment-related Adverse Event	Grade of Event	Nivolumab and/or Ipilimumab
motor, sensory, encephalitis)	Grade 3	Off protocol therapy (exceptions as noted below) ¹
	Grade 4	Off protocol therapy
Fatigue	≤ Grade 1	No dose modification
	Grade 2	No dose modification
	≥Grade 3	Off protocol therapy (exceptions as noted below) ¹ – if fatigue is found related to endocrinopathy and clinical symptoms are managed with hormone replacement, patient resume therapy
	Grade 4	Off protocol therapy

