8.7 Monitoring and Management of Immune-mediated Adverse Reactions

Immune-mediated Enterocolitis

The clinical presentation of GI immune-related AEs included diarrhea, increase in the frequency of bowel movements, abdominal pain, or hematochezia, with or without fever. However, inflammation may occur in any part of the GI tract including esophagitis and gastritis. Fatalities due to GI perforation have been reported in clinical trials of ipilimumab.

Patients should be carefully monitored for GI symptoms that may be indicative of immune-related colitis, diarrhea, or GI perforation. Diarrhea or colitis occurring after initiation of ipilimumab therapy should be evaluated to exclude infectious or alternate etiologies. In clinical trials, immune-related colitis was associated with evidence of mucosal inflammation, with or without ulcerations, and lymphocytic infiltration.

Monitor patients for signs and symptoms of enterocolitis (such as diarrhea, abdominal pain, mucus or blood in stool, with or without fever) and bowel perforation (such as peritoneal signs and ileus). In symptomatic patients, rule out infectious etiologies and consider endoscopic evaluation to establish etiology and for persistent or severe symptoms. C.difficile toxin has been detected in several patients with colitis and may be an independent entity or may co-exist with ipilimumab induced inflammatory colitis.

Withhold ipilimumab and/or nivolumab dosing for any patients with enterocolitis pending evaluation; administer anti-diarrheal treatment and, if persistent evaluate with colonoscopy and initiate systemic corticosteroids at a dose of 0.5 mg/kg/day prednisone or equivalent.

Permanently discontinue ipilimumab and nivolumab in patients with severe enterocolitis and initiate systemic corticosteroids at a dose of 1 to 2 mg/kg/day of prednisone or equivalent. Upon improvement to Grade 1 or less, initiate corticosteroid taper and continue to taper over at least one month. In clinical trials, rapid corticosteroid tapering has resulted in recurrence or worsening symptoms of enterocolitis in some patients.

Patients have been treated with anti-TNF agents for persistent colitis not responding to steroids.

Please note autoimmune pancreatitis may cause abdominal pain and should be included in all evaluations. Enteritis may occur occasionally with other autoimmune events including hepatitis, pancreatitis, and endocrine insufficiency, which should be evaluated as clinically indicated.

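### For most Grade 3 events in Arm 2, Section 8.4 and Table 8.1 disagree on whether nivolumab may continue alone; the maximum delay and the Cycle 1-4 nivolumab interval are also stated inconsistently

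*Combined protocol and SAP*

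**What the plan says.** **Grade 3 events in Arm 2.** The opening of Section 8.4 states that, during induction, "patients with Grade 2 or 3 events requiring discontinuation of treatment with the combination may consider continuing treatment with single agent nivolumab" after recovery to baseline. It then adds: "However, patients with renal, CNS, or pulmonary toxicity must be removed from study". Section 8.4d follows the nivolumab-alone path through Cycle 4 into Cycle 5+, and says that permanent discontinuation of ipilimumab should agree with Table 8.1. That table has a single action column for nivolumab and/or ipilimumab. In several rows its Grade 3 entry reads "Off protocol therapy (exceptions as noted below", with a pointer to footnote 1; in others the removal carries no exception. Section 8.7 says "Permanently discontinue ipilimumab and nivolumab in patients with severe enterocolitis", and gives the same instruction for Grade 3-5 hepatotoxicity/pancreatitis.

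**Maximum delay.** Section 7.5e lists as a removal criterion "Treatment delay for any reason > 12 weeks", and Section 8.2b gives the same limit as 84 calendar days. Section 8.4b, for Arm 2, takes off all protocol therapy "Patients requiring a delay of > 6 weeks or who experience immune-related toxicity" that prevents tapering prednisone to 10 mg daily or less. Table 8.1 removes patients after more than 2 weeks for nausea, diarrhea, vomiting and neutropenia. Section 8.3e permits delays for prolonged steroid tapers with no stated limit, and non-drug-related gaps in ipilimumab beyond 6 weeks with Study Chair approval.

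**Nivolumab interval in Cycles 1-4.** Section 7.3 gives every 21 days. Section 8.4d describes Cycle 1-4 dosing as every 2 weeks.

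**The concern.** A site treating an Arm 2 patient with, say, a Grade 3 rash that has resolved finds one passage that permits nivolumab alone and another that ends protocol therapy. Opposite stop and continue instructions for the same toxicity are first a patient-safety problem.

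They also bear on interpretation. Section 2.0 states the main hypothesis as adding ipilimumab to continued PD-1 inhibition. Whether PD-1 blockade continues after a toxicity that ends the combination is therefore part of what Arm 2 represents. If that depends on the passage a site follows, exposure after toxicity varies for reasons that are neither clinical nor designed.

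**Working it through.** The plan has no figure of its own on this point, so the check sets the passages side by side and then bounds the number of patients.

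**1. Grade 3 event in Arm 2 during induction**

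| Place | Instruction |
|---|---|
| 8.4 opening | Nivolumab alone allowed after return to baseline, except after renal, CNS or pulmonary toxicity |
| 8.4d | Nivolumab alone at investigator discretion; an ipilimumab-only stop is to follow Table 8.1 |
| Table 8.1, subject to footnote 1 | Off protocol therapy: nausea, diarrhea, vomiting, other GI, neurologic, fatigue, skin |
| Table 8.1, no footnote 1 exception | Off protocol therapy: pulmonary, thrombocytopenia, neutropenia, renal, liver, infusion reaction, all other events |
| Footnote 1 | Spares manageable laboratory or electrolyte abnormalities; says nothing on nivolumab alone |
| 8.3e | Names nivolumab alone for Grade 2 only |
| 8.7 | Both drugs stopped for severe enterocolitis and Grade 3-5 liver or pancreatic toxicity |

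**2. Where the rules do not conflict.** Grade 3 renal, CNS and pulmonary events end therapy under both rules. Grade 3 fever, endocrine and amylase/lipase events are hold rows. Footnote 1 spares certain laboratory values. Grade 4 events, events after induction and events that do not return to baseline fall outside the Section 8.4 permission. The conflict covers the remaining Grade 3 events.

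**3. Does one reading remove it?** If Table 8.1 governs, the Grade 3 permission in Section 8.4 is almost empty. If the Section 8.4 opening governs, it overrides most Grade 3 rows and collides with Section 8.7. Section 8.4d refers to the table for the ipilimumab-only case, but no row stops ipilimumab alone. The closing note of Section 8.3e points to nivolumab-alone guidance that the table does not contain.

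**4. Delay limits in days.** 2 weeks = 14 days, 6 weeks = 42 days, 12 weeks = 84 days.
- A delay of 43-84 days in Arm 2 ends therapy under 8.4b but not under 7.5e or 8.2b.
- A delay of 15-42 days for nausea, diarrhea, vomiting or neutropenia ends therapy under Table 8.1 but under none of those three sections.
- A steroid-taper delay under 8.3e has no limit of its own.

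**5. Nivolumab interval.** Four 21-day cycles are 84 days. Section 7.3 gives 84/21 = 4 administrations, and the Section 9.2 calendar agrees (weeks 1, 4, 7 and 10). A 2-week interval over the same 84 days would be 84/14 = 6.

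**6. Patients who could meet the Grade 3 conflict.** Inputs: 63 Arm 2 patients (Section 11.1) and 55% Grade 3/4 treatment-related events with the combination (Appendix 18.1a, citing a trial in untreated melanoma).
- Ceiling, if 55% carried over: 0.55 x 63 = 34.65, about 35.
- The conflicting subset is smaller, by step 2, and its share is not given. Assumed shares: 0.20 x 63 = 12.6 (13); 0.30 x 63 = 18.9 (19); 0.40 x 63 = 25.2 (25).

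The documents give no rate for delays of 43-84 days.

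**7. Primary analysis.** Under Section 10.5, PFS runs from registration to progression, symptomatic deterioration or death, with censoring at last contact. A toxicity stop or a change to nivolumab alone is neither an event nor a reason for censoring. The log-rank test in Section 11.2 stays computable, and no sample-size figure changes.

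**The case against.** The best defence is that the regimen is clear where it matters. Section 7.3 fixes drugs, doses and cycles for every Arm 2 patient, and PFS is followed whatever happens to treatment. Discretion after toxicity is deliberate: both the 8.4 opening and 8.4d leave continuation to judgement, so even a reconciled text would not give uniform PD-1 exposure. All of this stands. It answers the inference that the regimen is undefined, or that the PFS result cannot be attributed to the assigned strategy. It does not answer the contradiction, because Table 8.1 takes away the choice that Section 8.4 offers.

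On delay, Sections 7.5e and 8.2b can be read as an outer cap, with 8.4b as a stricter Arm 2 rule and the table rows stricter still; removal at 6 weeks breaches neither general section. That reading is coherent, so this part is weaker than the Grade 3 conflict. But no section states the hierarchy, the 12-week limit is worded to cover any reason, and 8.3e sits awkwardly with 8.4b.

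A reader might illustrate the problem with Grade 3 colitis that resolves in week 8 of a delay. The example is poor: the Grade 3 diarrhea row, its 2-week limit and 8.4b all end therapy, as does 8.7 if the colitis is severe. Keeping that patient on nivolumab would mean setting several passages aside.

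**Conclusion.** The Grade 3 contradiction is real, and no passage resolves it. The delay limits lack a stated hierarchy, and the two nivolumab intervals differ outright. The consequence is conflicting instructions to sites, with PD-1 exposure after toxicity in Arm 2 depending on the passage followed. The case for correcting the text rests on that, not on any failure of the primary comparison.

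The number affected is unknown. About 35 of 63 is a ceiling that assumes the 55% rate from untreated patients applies here; 13-25 rests on assumed shares of 20-40%. A reader might go further and assume that 60-90% of those with Grade 3/4 events are Grade 3, giving 34.65 x 0.6 = 20.8 to 34.65 x 0.9 = 31.2, or 33-50% of the arm. The documents do not support this as a count of affected patients: they give no such split, and the total includes events on which the rules agree. A large share of Arm 2 is possible but not shown.

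**What to change.** Reconcile Sections 7.3, 7.5e, 8.2b, 8.3e, 8.4 (opening, b and d), Table 8.1 and 8.7. State which passage governs Grade 3 events, what the maximum delay is in each arm, and one Cycle 1-4 nivolumab interval. The clinical leads must decide the content; this review takes no view on which rule, limit or interval is right. If they want separate actions for the two drugs, Table 8.1 needs an entry for each; if not, naming the governing passage may suffice.

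In the primary report, tabulate how many Arm 2 patients stopped ipilimumab only and how many stopped both drugs. The Treatment Forms and Off Treatment Notices already required (Sections 7.4, 7.6 and 14.4) supply the data.

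Cost: a wording amendment and one extra table, with no added patients or procedures.

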7.7 Follow-Up Period

All patients will be followed until death or 3 years after registration, whichever occurs first.

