 - Hospitalization for \leq Grade 2 adverse events where the primary reason for hospitalization is to expedite the clinical work-up.
 - Patients with the following conditions where in the treating investigator's opinion continuing study drug administration is justified based on the potential for continued clinical benefit:
 - Patients treated with systemic steroids for less than 2 weeks without evidence of autoimmune disease requiring steroids treatment
 - Grade 2 skin rash treated with topical steroids for less than 4 weeks
 - Grade 2 ocular toxicity that has completely responded to topical therapy within 4 weeks
 - Endocrinopathies where clinical symptoms are controlled with appropriate hormone replacement therapy. **Note:** Ipilimumab may not be restarted while the patient is being treated with systemic corticosteroids except for patients on stable doses of hormone replacement therapy such as hydrocortisone.
- e. Allowance for ipilimumab dose delay
- In general, patients who meet criteria to resume ipilimumab will also have met criteria to resume nivolumab with ipilimumab, so it should be feasible to synchronize dosing of both drugs when resuming ipilimumab. In order to facilitate this, the dosing calendar days of nivolumab and ipilimumab may be adjusted within a +/- 5 day window, as long as consecutive nivolumab doses are given at least 12 calendar days apart.
 - If an ipilimumab dose is delayed beyond 6 weeks from the prior ipilimumab dose, then subsequent nivolumab doses should be rescheduled to maintain at least a 3-week interval between consecutive ipilimumab doses.

- Dosing delays to manage drug-related adverse events, such as prolonged steroid tapers, are allowed. Disease assessments should continue as per protocol even if dosing is delayed.
- Dosing delays resulting in no ipilimumab dosing for > 6 weeks that occur for non-drug-related reasons may be allowed if approved by the Study Chairs. Disease assessments should continue as per protocol even if dosing is delayed.
- In event of any Grade 2 adverse event experienced while on combination nivolumab plus ipilimumab therapy, patient may resume treatment/may be continued on nivolumab monotherapy alone, at the discretion of the treating investigator
- Ipilimumab will not be given as monotherapy for Arm 2.

NOTE: If adverse events result in permanent discontinuation of ipilimumab, then subsequently manage dose delays under Management/Next Dose for nivolumab alone

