14.0 DATA SUBMISSION SCHEDULE

14.1 Data Submission Requirement

Data must be submitted according to the protocol requirements for **ALL** patients registered, whether or not assigned treatment is administered, including patients deemed to be ineligible. Patients for whom documentation is inadequate to determine eligibility will generally be deemed ineligible.

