14.4 Data Submission Overview and Timepoints

- a. WITHIN 24 HOURS AFTER BASELINE blood COLLECTION:

Submit Blood within 24 hours of collection at baseline, as outlined in [Section 15.0](#).

- b. WITHIN 7 CALENDAR DAYS AFTER REGISTRATION:

Submit the following:

S1616 Onstudy Form

S1616 Baseline Abnormalities Form

Baseline Tumor Assessment Form (RECIST 1.1)

Pathology Report documenting histologic confirmation of melanoma*

Submit radiology reports from all scans performed to assess disease at baseline.*

*NOTE: Upload reports via the Source Documentation: Baseline form in Rave®.

- c. WITHIN 21 to 35 CALENDAR DAYS AFTER REGISTRATION:

Submit tissue specimens as outlined in [Section 15.0](#).

Note: Blood for PBMCs must be submitted **within 24 hours of collection** at Day 28 (+/-) 7 calendar days.

- d. WITHIN 14 CALENDAR DAYS AFTER EACH CYCLE OF TREATMENT

Submit the following:

S1616 Treatment Form

S1616 Adverse Event Form

e. WITHIN 14 CALENDAR DAYS AFTER EACH DISEASE ASSESSMENT UNTIL PROGRESSION/RELAPSE (SEE STUDY CALENDAR FOR SCHEDULE):

Submit the following:

Follow Up Tumor Assessment Form (RECIST 1.1)

Submit radiology reports from all scans performed to assess disease.*

*NOTE: Upload reports via the Source Documentation: Follow-Up form in Rave@.

f. WITHIN 14 CALENDAR DAYS AFTER DISCONTINUATION OF TREATMENT:

Submit the following:

S1616 Off Treatment Notice

S1616 Treatment Form

S1616 Adverse Event Form

g. WITHIN 14 CALENDAR DAYS AFTER PROGRESSION:

Follow Up Tumor Assessment Form (RECIST 1.1)

Submit radiology reports from all scans performed to assess disease.*

*NOTE: Upload reports via the Source Documentation: Follow-Up form in Rave@.

h. AFTER PROGRESSION, SUBMIT EVERY 6 MONTHS FOR THE FIRST 2 YEARS AND THEN ANNUALLY UNTIL 3 YEARS FROM REGISTRATION:

Submit the following:

Advanced Melanoma Follow Up Form

Late Effects Form (if prior to treatment for progression or relapse or a second primary, and prior to non-protocol treatment, the patient experiences any severe [Grade \geq 3] long term toxicity that has not been previously reported)

i. WITHIN 4 WEEKS AFTER KNOWLEDGE OF DEATH:

Submit the Notice of Death documenting death information.

Also submit:

If the patient was still on protocol treatment, the materials specified in [Section 14.4e](#).

or

Advanced Melanoma Follow-Up Form (if the patient was off protocol treatment)

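### Section 8.4 takes Arm 2 patients with renal, CNS or pulmonary toxicity off study where it should say protocol therapy, and Section 8.3e lacks the matching organ exception

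*Combined protocol and SAP*

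**What the plan says.** Section 8.4 (Arm 2) opens with "For the initial induction period, patients with Grade 2 or 3 events requiring discontinuation of treatment with the combination" and lets such patients consider nivolumab alone once the event has resolved to baseline. The next sentence makes an exception: "patients with renal, CNS, or pulmonary toxicity must be removed from study".

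Section 8.3e, under the Arm 1 heading but written partly for the combination, gives a broader permission. Its condition is "In event of any Grade 2 adverse event experienced while on combination nivolumab plus ipilimumab therapy", and its consequence is "patient may resume treatment/may be continued on nivolumab monotherapy alone, at the discretion of the treating investigator". It names no organ exception and does not refer to Section 8.4.

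On follow-up, Section 7.7 states: "All patients will be followed until death or 3 years after registration, whichever occurs first". Section 14.1 requires data on all registered patients, "whether or not assigned treatment is administered, including patients deemed to be ineligible". Section 14.4e asks for tumor assessment forms and radiology reports "WITHIN 14 CALENDAR DAYS AFTER EACH DISEASE ASSESSMENT UNTIL PROGRESSION/RELAPSE". For dosing delays, Section 8.3e adds: "Disease assessments should continue as per protocol even if dosing is delayed". Section 8.4 has no such sentence for patients who are removed.

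**The concern.** There are two wording faults in operative instructions.

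**Removal.** Leaving treatment and leaving the study are different things. The first keeps the patient under observation for PFS, survival and late toxicity; the second does not. Section 8.4 uses the stronger term, in mandatory form, and only for Arm 2. A site that obeyed it would stop collecting primary endpoint data on patients selected by toxicity in one arm.

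**Nivolumab alone.** For a Grade 2 renal, CNS or pulmonary event that stops the combination, Section 8.3e allows nivolumab alone at the investigator's discretion and Section 8.4 rules it out. The choice is whether to give more anti-PD-1 treatment after, for example, pneumonitis or nephritis. A site should not have to work out which section takes precedence.

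**Working it through.** The plan states no figure on this point, so there is none to reproduce. The check is a comparison of texts followed by short arithmetic.

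**1. What toxicity leads to elsewhere in the protocol**
- Section 7.5 concerns removal from protocol treatment. It lists unacceptable toxicity and refers to Section 8.0 for detail.
- Section 8.4b, in the same section as the disputed sentence, sends patients off protocol therapy.
- Table 8.1, pulmonary row: a Grade 2 event needing steroids means removal from protocol therapy; Grade 3 and 4 mean off protocol therapy.
- Table 8.1, renal and neurologic rows: Grade 3 and 4 mean off protocol therapy, with listed exceptions for Grade 3 neurologic events.

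The wording in Section 8.4 is therefore the odd one out. Sections 7.7 and 14.1 contain no toxicity exception that would make the literal reading workable.

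**2. Sections 8.3e and 8.4 on nivolumab alone**
- Section 8.3e: any Grade 2 event on the combination; permissive; no organ exception.
- Section 8.4: Grade 2 or 3 events that require stopping the combination; nivolumab alone permitted, then excluded for renal, CNS and pulmonary toxicity; mandatory.
- Overlap: Grade 2 renal, CNS or pulmonary events that require stopping the combination. Here one text permits and the other forbids.

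**3. Timing, if Section 8.4 were followed literally**
- Induction without delays: 4 cycles × 21 days = 84 days = 12 weeks (Sections 7.3 and 7.4).
- First post-baseline disease assessment: completion of Week 12, i.e. day 84 (Section 9.2, footnote M).
- A patient removed before that scan has no scheduled post-baseline scan.
- PFS is then censored at last contact unless progression, symptomatic deterioration or death is already on record (Section 10.5).
- Response is counted as non-response, because patients with inadequate assessments stay in the denominator (Section 11.3).

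**4. Size per patient for response**
- Section 11.3 includes all randomized patients, so the denominator is the randomized number, not the 63 of the design.
- Planned accrual of 94 at 3:1 gives 94 × 3/4 = 70.5 in Arm 2.
- 1/70.5 = 1.42%, or about 1.4 percentage points. This is a ceiling: it applies only if the patient would otherwise have responded, and is zero if not.

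**5. Side check on power**

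A log-rank simulation used 63 versus 21 patients, medians of 6 and 3 months, 24 months of accrual, analysis at 36 months, a futility look at 41 events and one-sided 10%. The documents give no removal rate, so rates were assumed. With none, 5%, 10% or 20% of Arm 2 patients censored at random in the first 3 months, power was 91.9%, 92.0%, 92.4% and 90.9%. The no-loss value differs from the plan's 89%, and not all of the plan's simulation settings are given. Only the comparison across rows is of use, and only for loss unrelated to outcome.

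**The case against.** The strongest reply is that the protocol read as a whole already settles both matters. Section 7.5 classes Section 8 toxicity as a reason to leave treatment. Sections 7.7 and 14.1 and the calendars require follow-up without qualification. The disputed word is then a slip, harmful only if a site overlooks several plain instructions. On nivolumab alone, a general permission and a specific mandatory exception can be read together. A site that obeys Section 8.4 breaches nothing in Section 8.3e, and Section 8.4 introduces its organ rule as a limit on its own nivolumab-alone option.

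Most of this stands, and it is why the point is minor. It does not remove the point: Section 8.4 is a mandatory instruction that cannot be carried out literally alongside Section 7.7, and no text says that it overrides Section 8.3e.

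The no-scan consequence also has limits. Doses are often held before treatment is stopped, and assessments stay on schedule during delays. A patient removed late in a prolonged induction may already have had the Week 12 scan. The statement holds only for removal before that scan.

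The absence of a parallel sentence in Arm 1 is not itself a fault, since Arm 1 has no nivolumab-alone option to restrict.

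A reader might also infer that Table 8.1 contradicts Section 8.4, because it lets some Grade 2 renal, neurologic and pulmonary events be held and resumed. It does not: the Section 8.4 sentence qualifies events that already require stopping the combination.

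**Conclusion.** Both wording faults are real and can be seen on the page. Section 8.4 should speak of protocol therapy, and Section 8.3e should carry the organ exception. The Section 8.3e mismatch is a matter of patient safety instructions; the Section 8.4 term is a matter of follow-up.

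The follow-up consequence is conditional on a site taking Section 8.4 literally and on removal before the Week 12 scan. Each such patient would lack a scheduled post-baseline scan, would be censored for PFS at last contact unless an event was already recorded, and would lower the Arm 2 response rate by at most about 1.4 points, assuming planned accrual and the 3:1 ratio.

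A reader might go further and infer that the plan builds in one-sided censoring that biases PFS, or that power or type I error is impaired. The documents do not support this. They require follow-up of everyone, give no rate of such removals, and give nothing that links these toxicities to progression. The size of any bias cannot be computed, and no effect on power or type I error is claimed. Confidence in the textual finding is high; whether any site would act on the literal wording is unknown. Severity: minor.

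**What to change.** In Section 8.4, replace the clause with: *patients with Grade 2 or 3 renal, CNS, or pulmonary toxicity requiring discontinuation of the combination must be removed from protocol therapy; disease assessments and follow-up continue per Sections 7.7 and 9.0.*

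In the Grade 2 bullet of Section 8.3e, add: *except renal, CNS or pulmonary toxicity requiring discontinuation of the combination (see Section 8.4).*

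The cost is two clauses. Sections 7.7, 9.0 and 14.4e already require the visits, scans and data. The pages carry a closed stamp; if enrolment has ended, the sponsor can instead confirm that any Arm 2 patient taken off for these toxicities stayed in follow-up.
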